3.3 INTERVENTION

As of September 18th, 2018, enrollment into arm A of the study was discontinued due to concerns about tolerability of the medication. Enrollment into arm B of the study will continue until we reach the target sample size for this arm (N=8).

Eligible participants will be randomly assigned into one of two study arms: 1) 4.5 mg naltrexone or 2) 18mg nalmefene. Study medication will be provided by trained physicians, who will instruct participants in proper medication administration and adherence.

Drug capsules containing naltrexone hydrochloride (4.5mg) and nalmefene hydrochloride dihydrate (18mg) will be prepared by NonStopPharma, a compounding pharmacy in St. Petersburg, Russia. Doses will look identical; participants and providers will be blinded to assigned medication. Both medication capsules will include Riboflavin. Participants will be instructed to take one capsule orally once per day for 8 weeks. Participants will be given 28 days' worth of medications, with instructions to bring pill bottles/leftover medications to the following visit. Although medication visits will occur every two weeks, providing participants with 28 days of medications will ensure that they will not run out even if they miss the 2 and 6 week visits.

The Food and Drug Administration (FDA) has indicated that an Investigational New Drug (IND) is not needed for studies conducted outside the United States.

3.3.A. NALTREXONE

Participants randomized to this group will receive low-dose naltrexone for 8 weeks.

Participants will be instructed to take the medication once daily for 8 weeks. Naltrexone dosing will start on the day of the baseline visit, after successful passing of the naloxone challenge. If the participant does not pass the naloxone challenge, they will be brought back within a week to try again.

The most common side effects (reported in more than 1 in 10 people) of naltrexone are difficulty sleeping, anxiety, nervousness, abdominal pain/cramps, nausea and/or vomiting, low energy, joint and muscle pain, and headache.

Uncommon side effects (reported in less than 1 in 10 people, but more than 1 in 100 people) of naltrexone are loss of appetite, diarrhea, constipation, increased thirst, increased energy, feeling down, irritability, dizziness, skin rash, delayed ejaculation, decreased potency, and chills.

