Medication inserts will be provided to participants at baseline.

Medication distribution will be as follows:

Naltrexone:

- 28 capsules/bottle

- Participants will receive 1 bottle of 28 capsules at baseline and week 2.

Nalmefene:

- 28 capsules/bottle
- Participants will receive 1 bottle of 28 capsules at baseline and week 2.

Medication bottles will also be labeled. The medication labels will contain the following information:

FOR CLINICAL TRIAL USE ONLY

NALTREXONE/NALMEFENE

STORAGE: Don't store medication above 25°C.

KEEP OUT OF REACH OF CHILDREN AND PETS.

Return all unused medication to the study site.

DATE OF MANUFACTURE:

SHELF LIFE:

3.4.D. LOST OR STOLEN STUDY MEDICATION

If participants report lost or stolen medication, they will be provided with extra study medication. If participants report losing medication more than once, the study team will be alerted and the case discussed to determine a plan of action.

3.4.E. DISCONTINUATION OF STUDY MEDICATION

If as a result of study testing at week 4, a participant is found to have AST/ALT >10x normal, medications will be discontinued and the participants will be appropriately monitored for resolution of the abnormalities. If a participant has AST/ALT >5x normal as a result of study testing at week 4, participant will be rechecked at their 6-week visit to ensure levels do not increase to the threshold of discontinuation. Any participant with symptoms of acute hepatic failure (jaundice, dark urine) will have AST/ALT checked.

Those who discontinue medication will be followed and analyzed by intention to treat.

Participants found to be pregnant during the study will have their study medication discontinued, but will still be followed-up for the duration of the study. Participants who report pregnancy outside of study visits will be instructed to immediately discontinue their study medication and requested to come in for a confirmatory urine pregnancy test.

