3.5 SCHEDULE OF DATA COLLECTION

		Screen	Baseline Visit	2 week visit	4 week visit	6 week visit	8 week visit
Screening	Screening Questions	X					
	Verification of HIV, non-pregnancy, urine tox, and ALT/AST	X					
Enrollment	Sign Informed Consent	X					
	Complete contact information/verify numbers	X					
	Randomization		X				
Laboratory	Clinical Values		X		X		X
	Pregnancy Test	X	X	X	X	X	
	Urine Drug Test	X	X				
	AST, ALT	X			X	X (if indicated)	X
	Cold Pressor Test		X		X		X
	Naloxone Challenge		X				
Assessment	Full Study Assessment		X		X		X
	Short Assessment			X		X	
Intervention	Symptom Management/Adverse Events		X	X	X	X	X
	Provide Medication Instructions		X				
	Give Study Medication		X	X			
	Discuss Adherence		X	X	X	X	
	Assess Adherence			X	X	X	X
Other	Provide Resource Card		X				
	Compensate for Participation	X	X	X	X	X	X
	Report Adverse Events		X	X	X	X	X
	Complete Tracking Forms	X	X	X	X	X	X

3.5.A. VISIT WINDOWS

Baseline Visit

- Window open: 1 day post screening
- Target date: 3 days post screening
- Window close: 28 days post screening
- Window length: 27 days

2 Week Visit

- Window open: 7 days post baseline
- Target date: 14 days post baseline
- Window close: 20 days post baseline

- Window length: 13 days

4 Week Visit

- Window open: 21 days post baseline
- Target date: 28 days post baseline
- Window close: 34 days post baseline
- Window length: 13 days

6 Week Visit

- Window open: 35 days post baseline
- Target date: 42 days post baseline
- Window close: 48 days post baseline
- Window length: 13 days

8 Week Visit

- Window open: 49 days post baseline
- Target date: 56 days post baseline
- Window close: 62 days post baseline
- Window length: 13 days

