4.4 VISIT FLOW

Pre-screen (optional):

- Screening questions administered over the phone

Screening visit:

- Screening Questions
- Informed Consent and Enrollment
- Conduct HIV, urine drug test, draw blood for AST/ALT testing (if recent test result not provided), and pregnancy testing
- Compensate participant, collect locator/contact information and check contact phone numbers
- Schedule return visit, if eligible
- Provide resource document, appointment reminder card

Baseline visit:

- Review and update locator/contact information, verifying new numbers, as necessary
- Conduct urine drug testing and pregnancy testing
- Administer naloxone challenge
- Administer assessment questionnaire
- Assess baseline symptoms
- Randomize participant
- Conduct cold-pressor test
- Introduce study medication and instructions and develop an adherence plan
- Provide study medication
- Compensate participant; provide appointment reminder card, participation card, daily diary, and schedule next visit

2- and 6-week medication visit:

- Review and update locator/contact information, verifying new numbers, as necessary
- Collect a urine sample to check for pregnancy and adherence
- Administer a brief assessment of tolerability and side effects
- Assess medication adherence
- Provide study medication (2-week visit)
- Compensate participant and schedule next visit

4- and 8-week full study visit:

- Review and update locator/contact information, verifying new numbers, as necessary
- Collect a urine sample to check for pregnancy (4-week only) and adherence
- Assess medication adherence
- Administer assessment questionnaire
- Conduct cold-pressor test
- Compensate participant and schedule next visit (4-week only)

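### Section 3.3 says missing weeks 2 and 6 cannot exhaust the supply, but the second and last bottle is scheduled only at week 2, so missing that visit can end dosing at day 27

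*Combined protocol and SAP*

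**What the plan says.** Section 3.3 sets the regimen: "Participants will be instructed to take one capsule orally once per day for 8 weeks". It adds that supplying 28 days at a time "will ensure that they will not run out even if they miss the 2 and 6 week visits".

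Three operational passages set the dispensing times:

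- Section 3.4.C, in the same words for each arm: "Participants will receive 1 bottle of 28 capsules at baseline and week 2".
- Section 3.5, the row "Give Study Medication", marked at baseline and week 2 only.
- Section 4.4, under the week-2 and week-6 visits: "Provide study medication (2-week visit)". The list for weeks 4 and 8 has no dispensing step.

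The only rule for additional supply is in section 3.4.D: "If participants report lost or stolen medication, they will be provided with extra study medication". The week-2 window runs from day 7 to day 20 (section 3.5.A: "Window close: 20 days post baseline"), and the week-4 window opens on day 21.

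Section 2.2 makes the week-8 tolerability score primary, rated over the preceding two weeks. It defines discontinuation as self-reported stopping at any time in the treatment period. Section 8.1 analyses everyone who took at least one dose.

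**The concern.** The assurance in section 3.3 covers two visits and fails for one of them. The second bottle is tied to week 2, so a participant who misses that visit has only the first bottle, and no instruction says when the second is to be handed over.

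This reaches the main result in two ways. First, the week-8 score may describe a period with no drug on board. The plan does accept off-drug scores from people who stop (section 3.4.E: "Those who discontinue medication will be followed and analyzed by intention to treat"), but stopping by choice may reflect intolerance, whereas a supply gap says nothing about it. Second, the definition of discontinuation does not separate running out from choosing to stop. Section 2.7.A uses both mean tolerability below 80 and a larger than expected discontinuation percentage in deciding whether to go on to the UH3 phase. With so few participants per arm, one case carries weight.

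**Working it through.** **Inputs.** One capsule daily for 8 weeks, 28 capsules per bottle (3.3, 3.4.C). Dosing starts on the baseline day, taken as day 0 (3.3.A, 3.3.B). Visit windows are days 7-20 for week 2, 21-34 for week 4, 35-48 for week 6 and 49-62 for week 8, with targets at days 14, 28, 42 and 56 (3.5.A). Recall is read as the 14 days before the visit, visit day excluded.

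**The plan's own supply.** 2 × 28 = 56 capsules for 8 × 7 = 56 days. With the second bottle issued anywhere on days 7-20, the last dose falls on day 55 and all 56 doses are covered. Missing week 6 changes nothing, because no bottle is due then.

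**Week 2 missed, no later dispensing.** Bottle 1 covers days 0-27. The first missed dose is day 28, and 56 − 28 = 28 doses (50%) are not supplied. For a visit on day d the recall period is days d−14 to d−1, so the on-drug days in it are:

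| Visit | Visit day | Recall days | On-drug days |
|---|---|---|---|
| Week 4 | 28 (target) | 14-27 | 14 |
| Week 4 | 34 (close) | 20-33 | 8 |
| Week 6 | 35 (open) | 21-34 | 7 |
| Week 6 | 42 (target) | 28-41 | 0 |
| Week 8 | 49 (open) | 35-48 | 0 |
| Week 8 | 56 (target) | 42-55 | 0 |
| Week 8 | 62 (close) | 48-61 | 0 |

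**Sensitivity to missed doses.** Skipped doses stretch the bottle. At adherence a, evenly spaced, 28 capsules last 28/a days. They reach into the week-8 recall only if 28/a > d − 14, that is, if a < 28/(d − 14):

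- d = 49: 28/35 = 80%
- d = 56: 28/42 = 66.7%
- d = 62: 28/48 = 58.3%

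The zero therefore holds for fairly regular dosing, not for every participant.

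**Second bottle issued at the week-4 visit on day v, dosing stopped at day 55.** Gap = max(0, v − 28).

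| v | Gap (days) | Doses taken |
|---|---|---|
| 21-28 | 0 | 56 |
| 29 | 1 | 55 |
| 34 | 6 | 50 |

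On-drug recall days at week 8 are then 14 at visit days 49-56 and 8 at day 62 (days 48-55), the same as for a participant who attended week 2.

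**Weight of one case.** With the 7 evaluable per arm assumed in section 2.7.A, one participant carries 1/7 = 14% of the arm mean. With 8 per arm, one run-out counted as discontinuation adds 1/8 = 12.5 percentage points. The documents do not say how an off-drug rating would differ. If it differed by 10, 20 or 40 points (assumed values), one such participant would move a mean of 7 by 1.4, 2.9 or 5.7 points.

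**The case against.** The textual conflict and the arithmetic are not in serious dispute; the consequence is. Three things must coincide: no contact on days 7-20, near-daily dosing and no resupply. The third is the weakest. Treatment is stated to last 8 weeks, leftover capsules are counted at each follow-up visit, and section 3.3 shows the intent that a missed week 2 should not cause a run-out. Staff at week 4 would have to see an empty bottle, hold the undispensed one and not issue it.

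The trigger is also mitigated. No-shows are rescheduled and transport is arranged where needed (4.7), week 2 is paid (4.6), and a participant seen on days 21-27 still has capsules. No rate of missed week-2 visits is given. A shift of 2.9 points from one participant is small beside the plan's confidence-interval half-width of 11.2 (22.4/2). The go/no-go judgement on discontinuation is qualitative, so the team could discount a run-out it knew about. This is a 16-person study without formal testing, and enrolment into arm A has stopped.

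Most of this stands as a limit on the likely size of the harm. It does not rescue the sentence in section 3.3. Rescheduling governs appointments, not bottles. Once day 20 has passed, the next scheduled visit lists no dispensing, and extra supply is described only for loss or theft. Resupply would depend on staff departing from three consistent instructions. The section 7.4 form list does appear to mark a medication visit checklist at week 4, but it does not say that medication is given then.

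**Conclusion.** The concern holds. The assurance in section 3.3 is wrong as written for a missed week-2 visit and harmless for a missed week-6 visit. If week 2 is missed, capsules are taken daily and no bottle is issued later, supply ends at day 27, half of the planned doses are not supplied, and the primary rating covers no on-drug days anywhere in the week-8 window.

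That result depends on all three conditions. Adherence below about 58% to 80%, depending on the visit day, would carry some capsules into the recall period. The number of participants affected and the direction of any bias are unknown, so no effect on the tolerability mean or the UH3 decision is claimed. Tolerability is also collected at weeks 2, 4 and 6, and under daily dosing a week-4 score at the day-28 target is still fully on drug, so some usable information would remain. The correction should be made because it is cheap and protects the primary measure.

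**What to change.** Amend sections 3.4.C, 3.5 and 4.4 to say that a second bottle not collected at week 2 is issued at the next contact, by day 28 if possible and at the week-4 visit at the latest. State that dosing still ends at 8 weeks and that leftover capsules are returned, as the label already asks. A week-4 visit on days 29-34 leaves a gap of 1 to 6 days, so section 3.3 should be reworded to promise no more than this rule delivers.

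A useful but optional addition is a reason code that records a supply run-out separately from participant-chosen discontinuation.

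The cost is one sentence in each of three dispensing passages, the rewording in 3.3 and, if adopted, one code. No extra capsules, visits or weeks of dosing are needed. The week-4 visit already includes a pregnancy test, a symptom check and a capsule count. With arm A closed to enrolment, the benefit falls mainly on the remaining arm B participants.

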3.4 MEDICATION CONSIDERATIONS

3.4.A SYMPTOM MONITORING

The study staff (research clinicians [addiction physicians with extensive experience performing pharmacotherapy trials]) will provide participants with the correct medication packages and advice on how to take the capsules. The staff will be trained to assess for adverse medication effects and will follow established protocols for identifying and monitoring any ongoing adverse events, including referral to treatment as appropriate. Study participants will be actively monitored for adverse events. Symptoms will be assessed every two weeks (and monitored more frequently, if necessary) by trained clinical staff,

while the participants are administered study medications. Processes have been set up to address any adverse event brought to the attention of study staff during the trial.

3.4.B. ADHERENCE

As one of the study outcomes, medication adherence will be assessed at each study visit using the direct (Riboflavin) and indirect (capsule counts and self-report) measures.

Direct Adherence Measures

Riboflavin (50 mg), a vitamin yielding a change in urine color, will be added to both study medications. Participants will be informed that the color change is harmless. At this dose, Riboflavin is expected to remain in the system at detectable levels for up to 24 hours. At each study visit post-baseline (while taking study medication), participants will be asked to provide a urine sample which will be visually inspected for the presence or absence of Riboflavin in a room with low ambient light, using ultraviolet (UV) light at the long wave setting (33 nm).

Indirect Adherence Measures

Capsule Counts

Participants will be instructed to bring any unused medication to each study visit post-baseline. The RA will count and record the number of remaining capsules. We will extrapolate the amount of medication taken and determine the measure of adherence.

Self-Report

Medication adherence will also be measured through self-report using the modified Adult AIDS Clinical Trial Group (AACTG) ART adherence questions.

Adherence Aids

During each study visit medication instructions will be reviewed and strategies for adherence discussed with each participant. Adherence plans will be individually tailored to each participant, depending on his or her reason for non-adherence.

Participants will also be encouraged to set a reminder in their phone to take the study medication each day.

3.4.C. MEDICATION DISBURSEMENT

Medication inserts will be provided to participants at baseline.

Medication distribution will be as follows:

Naltrexone:

- 28 capsules/bottle

- Participants will receive 1 bottle of 28 capsules at baseline and week 2.

Nalmefene:

- 28 capsules/bottle
- Participants will receive 1 bottle of 28 capsules at baseline and week 2.

Medication bottles will also be labeled. The medication labels will contain the following information:

FOR CLINICAL TRIAL USE ONLY

NALTREXONE/NALMEFENE

STORAGE: Don't store medication above 25°C.

KEEP OUT OF REACH OF CHILDREN AND PETS.

Return all unused medication to the study site.

DATE OF MANUFACTURE:

SHELF LIFE:

3.4.D. LOST OR STOLEN STUDY MEDICATION

If participants report lost or stolen medication, they will be provided with extra study medication. If participants report losing medication more than once, the study team will be alerted and the case discussed to determine a plan of action.

3.4.E. DISCONTINUATION OF STUDY MEDICATION

If as a result of study testing at week 4, a participant is found to have AST/ALT >10x normal, medications will be discontinued and the participants will be appropriately monitored for resolution of the abnormalities. If a participant has AST/ALT >5x normal as a result of study testing at week 4, participant will be rechecked at their 6-week visit to ensure levels do not increase to the threshold of discontinuation. Any participant with symptoms of acute hepatic failure (jaundice, dark urine) will have AST/ALT checked.

Those who discontinue medication will be followed and analyzed by intention to treat.

Participants found to be pregnant during the study will have their study medication discontinued, but will still be followed-up for the duration of the study. Participants who report pregnancy outside of study visits will be instructed to immediately discontinue their study medication and requested to come in for a confirmatory urine pregnancy test.

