2.2 STUDY OUTCOMES

Primary Outcomes: The primary outcome for this study is tolerability of medication during treatment. Based on measurements used by other researchers, medication tolerability will be measured via a 0-100 visual analog scale with 0 anchored as “cannot tolerate at all” and 100 as “tolerate perfectly well.” Participants will be asked to estimated tolerability over the previous 2 weeks at each study visit: the primary outcome will be tolerability score at the week 8 visit.

Secondary Outcomes:

- 1) Alcohol reduction measured as a reduction in mean number of grams of pure ethanol consumed per day.
- 2) Treatment discontinuation: defined as patient self-report of stopping medication anytime during the treatment period. Participants will be instructed to notify the study staff in real-time if they discontinue medications, and they will be queried about discontinuation at the week 4 and 8 study visit assessments. Lost-to-follow-up will be assumed to be equivalent to treatment discontinuation.
- 3) Adherence: defined as self-report of the percentage of study medications taken in the past 2 weeks, using a visual analog scale (VAS) from 0 to 100, same as used to assess adherence to HIV medication. Participants will be asked to mark on the ruler what percentage of medication they have taken that week ("0% means no medication, 50% means half your medication, 100% means all your medication"). In addition, medication adherence will be assessed by Riboflavin (50 mg) that will be included in the capsules by the pharmaceutical laboratory. This allows for assessment of medication adherence in both medication arms. Visual inspection of the urine for the presence or absence of riboflavin using ultraviolet (UV) light at the long wave setting (33 nm) in a room with low ambient light will be conducted.
- 4) Reported side effects. We will use a Symptom Checklist based on side effects reported in prior studies of naltrexone, plus an open-ended question to assess for any side effects from study medications in the past 4 weeks at visits 4 and 8. Participants side effects will be rated by trained research assessors, using the Guidelines for Severity Grades (mild, moderate, severe, and life-threatening, death) (See Box 1).
- 5) Medication Satisfaction: This 14-item questionnaire assesses satisfaction with medication to treat chronic conditions and difficulty/inconvenience of use.

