2.3 STUDY DESIGN

This is a randomized, double-blinded, 2-arm study of 16 participants with HIV, chronic pain (defined as any bodily pain of moderate to severe intensity lasting for ≥ 3 months), and past-year heavy alcohol use, defined by NIAAA criteria. The 16 participants will be randomly assigned to either naltrexone or nalmefene with a 1:1 allocation ratio using permuted blocks to ensure equal numbers in each arm. Although we will not be formally testing differences between the naltrexone and nalmefene groups, participants will be randomized to the 2 arms in order to minimize selection bias and confounding in the allocation of interventions. Participants will be treated for 8 weeks, and outcomes (tolerability, alcohol use, side effects, medication adherence and discontinuation, and willingness/desire to continue to take medication at the end of study) will be evaluated at the end of treatment. In addition, we will review changes in pain during treatment with naltrexone and nalmefene to ensure that pain does not get worse and determine whether there is some improvement.

The study design and schedule for study visits and assessments is depicted in Figure 1. After consent and enrollment participants will be randomly assigned to either low-dose naltrexone or standard-dose nalmefene. The schedule of study in-person visits/assessments are as follows: screening visit, baseline, 2, 4, 6, and 8 weeks. At baseline, weeks 4 and 8, full study visits will occur, including assessments of tolerability of medication, medication discontinuation, treatment side effects, self-reported adherence and confirmation of adherence through riboflavin urine testing, self-reported pain, and experimental cold pain tolerance (cold-pressor test). Participants will also be instructed to keep a daily dairy to record pain severity, medication adherence, and alcohol use. Weeks 2 and 6 will be short visits at which time a brief assessment of tolerability, side effects, and adherence will occur. Throughout the course of the study, participants will be expected to come in for three in-person assessments and blood draw visits (screening/baseline, 4- and 8-weeks) and two shorter in-person visits.

Figure 1: Study Design (UH2 Phase)

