3.6 DATA SOURCES

3.6.A QUESTIONNAIRES

Questionnaires will be administered at baseline, 2-, 4-, 6-, and 8-week study visits. At weeks 4 and 8, assessments of tolerability of medication, medication discontinuation, treatment side effects, self-reported adherence, and self-reported pain will occur. At weeks 2 and 6, brief assessment of tolerability, side effects, and adherence will occur.

3.6.B. URINE

A pregnancy test will be administered by trained clinical research staff at screening to determine eligibility and at each study visit (except for 8-weeks).

Pregnant women will be excluded from the study due to some reports suggesting possible adverse events with study medications. Participants found to be pregnant will discontinue their study medication but will still be followed-up for the duration of the study.

Urine will also be checked at screening and baseline, as part of the naloxone challenge, to ensure that participants have not recently used opiates (as opioid receptor antagonists would be contraindicated as they could precipitate withdrawal). The urine drug test will test for a range of opioids, specifically opiates (products of the poppy plant – morphine, heroin) and synthetic opioids (specifically methadone).

If new opioids appear on the scene in Russia, such as fentanyl, then we will begin testing for this, but currently that is not thought to be an issue.

A urine sample will be collected from all participants at each study visit post-baseline while on study medication to be inspected for the presence or absence of Riboflavin, as a measure of medication adherence, as described in section 3.4b Adherence.

3.6.C. BLOOD

Blood will be collected at screening, 4- and 8-week study visits to assess AST/ALT levels. Blood may also be collected at the 6-week study visit for liver function testing, if indicated at the participant's 4-week study visit (see Section 3.4E).

3.6.D. COLD-PRESSOR TESTING

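### The riboflavin adherence reading has no pre-dose control, so a background positive cannot be told from capsule ingestion; separately, the stated lamp wavelength contradicts its own label

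*Combined protocol and SAP*

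**What the plan says.** Section 3.4.B of the combined protocol and SAP names riboflavin as the direct measure of adherence, with capsule counts and self-report as indirect measures. Each capsule in both arms carries 50 mg. On timing, 3.4.B says: "At each study visit post-baseline (while taking study medication), participants will be asked to provide a urine sample". Section 3.6.B agrees: "A urine sample will be collected from all participants at each study visit post-baseline while on study medication". The schedule in 3.5 marks adherence assessment from week 2 onwards, with nothing at baseline.

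Urine is nevertheless taken at baseline. The visit flow in 4.4 lists, ahead of the naloxone challenge, randomization and dispensing: "Conduct urine drug testing and pregnancy testing". The drug test applies to all participants.

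Section 2.3 is worded differently. It opens a list with "At baseline, weeks 4 and 8, full study visits will occur, including assessments of tolerability of medication" and later in the same sentence includes "confirmation of adherence through riboflavin urine testing".

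The urine is judged by eye as showing riboflavin or not. Section 2.2 describes the inspection as made "using ultraviolet (UV) light at the long wave setting (33 nm) in a room with low ambient light", and 3.4.B gives the same setting and the same figure. No reference urine or intensity cut-off is stated. Section 3.4.B expects riboflavin to be detectable for at most 24 hours after a dose.

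**The concern.** A present/absent reading needs some evidence of what it shows in people who have not taken the capsule. This plan has none. Both arms receive riboflavin and there is no placebo arm, so no participant on treatment shows what riboflavin-free urine looks like under this lamp. The participant's own pre-dose urine is the natural control; it is in hand at the baseline visit and is not read.

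The consequence is limited but real. Adherence is a secondary outcome, and section 2.7.A lists more non-adherence than expected among the qualitative grounds for not going on to UH3. A background positive taken as adherence would push that judgement towards proceeding.

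The second defect is in the test specification. A long-wave setting and a figure of 33 nm cannot both be right, and the pair appears in two sections.

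**Working it through.** **Is there a pre-dose reading?** Sections 3.4.B and 3.6.B both say post-baseline. The schedule in 3.5 and the baseline list in 4.4 contain no riboflavin step at baseline. Only the sentence in 2.3, read literally, would include baseline. That sentence also lists tolerability and discontinuation of medication, which cannot be assessed before the first capsule. It is loose wording and does not supply a control, but it conflicts with the operational sections and needs reconciling.

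**How much could background positives matter?** The plan states no sensitivity, background rate or positivity target, so there is no figure of its own to reproduce. What follows is illustrative. Let

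- a = true share of participants who dosed within the detection window (assumed),
- Se = probability that a dosed participant reads positive (assumed),
- f = probability that an undosed participant reads positive (assumed, 0.10 to 0.30).

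Then P(positive) = a × Se + (1 − a) × f.

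With Se = 1 the excess over a is (1 − a) × f:

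| a | f = 0.10 | f = 0.20 | f = 0.30 | Excess, f = 0.10 to 0.30 |
|---|---|---|---|---|
| 0.9 | 0.91 | 0.92 | 0.93 | 1-3 points |
| 0.7 | 0.73 | 0.76 | 0.79 | 3-9 points |
| 0.5 | 0.55 | 0.60 | 0.65 | 5-15 points |

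The excess is largest when adherence is poor. For scale, one participant in an arm of 8 is 1/8 = 12.5 points.

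**Is the net error upward?** Not necessarily. With a = 0.6 and Se = 0.8, P(positive) = 0.48 + 0.4 × f, which is 0.52 at f = 0.10 and 0.60 at f = 0.30. Across the whole assumed background range, the test then reads at or below the true 60%.

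**What could a baseline reading show?** If 0 of m baseline urines are positive, the upper limit of the exact 95% interval for f is 1 − 0.025^(1/m):

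- m = 8: 1 − 0.025^(1/8) = 36.9%
- m = 16: 1 − 0.025^(1/16) = 20.6%

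The chance of finding at least one positive among 8 is 1 − (1 − f)^8: 57% at f = 0.10 and 83% at f = 0.20. The reading can flag individuals but gives only a loose bound on the rate.

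**Wavelength.** The documents do not define long-wave UV. Taking it as roughly 315-400 nm (general physics, stated as an assumption), 33 nm is too small by a factor of 315/33 = 9.5 to 400/33 = 12.1.

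**The case against.** The case against acting is that riboflavin is one of several adherence measures in a small descriptive study without formal testing, and that a single spot reading adds little. Much of this stands, and it rules out several stronger readings that a reader might infer.

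- *That the wrong wavelength creates false positives.* Staff are told to use the lamp's long-wave setting. The figure looks like a misprint, and a misprint in the text does not alter what the urine shows. The two defects are independent.
- *That the error can only inflate adherence.* This is true of background positives but not of the test as a whole. Detection lasts at most 24 hours, dosing is once daily, and the reading is not tied to the time of the last capsule, so an adherent participant can read negative.
- *That nothing could identify another riboflavin source.* Sections 5.1 and 5.2 ask about prescription and non-prescription medication, and 6.2 has the medication list reviewed at every visit. Vitamins are not named and the list is not linked to the reading, but the route exists.
- *That a background positive enters the reported adherence figure.* Section 8.1 plans a mean percentage adherence, which fits the 0-100 self-report scale in 2.2 rather than a present/absent reading. It does not say that riboflavin contributes. Section 2.7.A is qualitative and sets no riboflavin threshold.

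Two limits on the remedy also stand. Section 3.3 records that arm A closed to enrolment and arm B continues to N=8, so participants already dosed cannot supply a control. A single baseline reading also cannot show background that first appears at weeks 2 to 8, for example from a vitamin product started later.

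What the objection does not answer is that the only direct measure has no negative control, although the material for one is collected before dosing.

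**Conclusion.** The point holds as two separate small defects.

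First, a positive riboflavin reading cannot be attributed to the capsule, because no pre-dose reading is made and both arms receive riboflavin. Such a positive may be taken as adherence in the qualitative UH3 judgement; the documents do not show that it will be. Any inflation from this source would be 1-3 points at 90% true dosing and 5-15 points at 50%. Those figures rest on an assumed background of 10-30%, perfect sensitivity and assumed levels of true dosing, none of which the documents give. With imperfect sensitivity the net error could be zero or downward.

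Second, the wavelength figure contradicts its label in 2.2 and 3.4.B. This is a specification error with no shown effect on any result.

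Neither defect threatens the primary outcome. Both are worth correcting because the corrections cost so little.

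**What to change.** 1. In 3.4.B, 3.6.B and 4.4, for participants not yet dosed, read the baseline urine already collected for the drug test under the same lamp and by the same rule. Do this before the first capsule and, following the order in 4.4, before randomization.
2. Flag baseline-positive participants. Report riboflavin positivity by visit with and without them, and state this summary in 8.1, which names none at present.
3. Check the medication list already reviewed at each visit for vitamin products, and note any beside the riboflavin result.
4. Reconcile the sentence in 2.3 that attaches riboflavin testing to the baseline visit with 3.4.B and 3.6.B.
5. In 2.2 and 3.4.B, replace 33 nm with the actual long-wave value of the lamp in use.

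The cost is protocol wording and one lamp reading per remaining participant on urine already in hand. The later readings of baseline-positive participants become uninformative. With about 8 to 16 participants at most, the baseline result should be reported as a count that flags individuals, not as an estimate of the background rate.
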